Urinalysis	×		X''				>	C X				X			3	2			X		_		X		_		X	×	X	X	X
Drug administration (MCS110 infusion) ^{14, 15}			~		×		-		×	_	-		×		-		c14	_		x	15	_		×	_	-					
MRI ⁴					 		_		l î	_	-		-			-		_	1.10	-	-	_	1.10	- ^	_		-	14	14	1.10	
MRP .		x			_		_	×	\rightarrow			X10		+	X	~	+	_	X···	$ \rightarrow $	_		X	_	_		-	×	×	X ¹⁰	×
Corporate Confidential Information		X ⁵															\square													×	X17
Corporate Confidential Information			X																									x			
	X		×					< X				X)	<			X				X				×	×	X	X	×
	X		X		-			< X				X	_	+ +	2	<			X		_		X	-	_		X	X	X	×	X
	X			×				X				X				<			X				X				×	X	×	X	×
				×	X		(⁸)	C X		X ⁶	X ^a	x	V ⁰		X ⁸ 2	2	×8.	- ×	8 X		¥8	~	X	- I - I	18	V ⁶	×	×	X	X	X
			×	X						^	X ⁶	X			xo			- 10			^	- 0			 	20	×		×	×	×
					-			 	+	_	^	^	_	+ +	~ /	`	+ +	- ^	^		-+		-	\rightarrow	-	^	~	-	^	^	
			×		_			_	+	_	-			+	_	_	+	_		$ \rightarrow $	_	_	+	_	_			×	_		
			×		_			_								_	$ \rightarrow $	_			_			_	_		-	×	_	-	
	×		×				>	< X				X)		$ \rightarrow $		X				X				×	X	X	×	×
			×						$ \rightarrow $					$ \rightarrow $)	<	$ \rightarrow $											×		×	×
			×																									×			
			X																												
	×		×	×				< X				X)	<			×				×				×	×	×	×	×
SAE reporting ⁹															×																
Adverse Event reporting®															X																
Study completion information																											- 1		1	1	x
Comments					_	_		_		_				35.0	quire	b d		_			_			_			_	_	_	_	

Novartis	Confidential	Page 47
Amended Protocol Version v07 (Clean)		Protocol No. CMCS110X2201

Assessment Schedule (Part C – Adults) Protocol Amendment 06

As a number of patients complete the study according to Protocol Amendment 06 –before Protocol Amendment 07 is approved - this assessment schedule is therefore being kept below.

			CMCS	110	X22	01 P	art	C	- As	sses	sm	ent	Scl	hed	ule																		
	Scre	enina	Baseline	_	_		_	_	_	_	_	_	_	Tre	atme	ent	_	_	_	_	_	_	_	_	_	_		_	Foll	ow-up		_	FOR
Visit Numbers ¹		1	2	-	3			4		5		-		6			7		-		8			9	,	_	10	44	12	13	14	15	777
Weeks		-	~	-			-	2		4		+		8	_		12		-	- 1	6	-		20		_	24		40		72	88	104
		-1	-				_	 		4				2	_		3				4	_	—	5		_							26
Months		-1 -21 to -8	-7 to -1	-			-	15		20		+		2 57	_		85		-		4			14		_							729
Study Day Allowed visit window (days)	- 28 to -22	-21 to -8	- 7 to - 1	-	- 1			13		±3		+		±5			±5		-		5	_	-	±5		_	±5	±8	±8	±8	±8	±8	
Time hrs	-	-		Drol.	0 4	2					2 6				1.6	prol (2 5	D.C.D.			1.6	D C D			1.6	10	70	10	10	20	10	10
Informed consent	×		-	016	 	+ + +	 	- 12	76 0	' ' 	 	1016			- ×	pre v	 		pre	-		- ×	Pre-	 	-		-	-	-	-	-	 	 
Inclusion / Exclusion criteria	×		×		_	++		_	_	+ +	_	-	+++	_	-		-	_			_				-					-		-	
Relevant med, hist, / Gurent med, cond.			×		_	+ +	_	-	_	+ +	_	+	++	_	-		-				_				-							-	
Demography	×							_				-	++				-			_	_				-							-	
Prior / concomitant medication(s)								_		_							;	< -		_		-		_									
Hepatitis B and C screen and HIV screen	X											1																					
Quantiferon TB test	×																																
Alcohol test, drug screen	×		X11						×			×				×			×				×					×					
FSH test (females only)	×																																
Pregnancy test (in serum, females only)	×																																×
Pregnancy test (urine, females only)			X11					X I	x			X				×			×				X				х	×					
Physical examination	×		×		_	++			x	+ +	_			_	-		-				-		X		-				×	×	×	×	×
Joint Range Of Motion	x		x					××	2 I			×				X			XX				X				×	×	X	×	×	×	×
Body height	×						-					1.1							- C -	_		-											
Body weight	×		×					×	x	+ +		X				x	-		X	_			X				×	x	X	×	×	×	×
Vital Gigna: Body temperature, Blood presaure, Pulse	X		X	X	X 2	X				X ²	XX	X	X 2	×	X	x	X 2	XX		X 2	×	×	X	ж ²	X	×	X	x	X	X	×	X	X
ECG evaluation 3	×		×	$\overline{\mathbf{v}}$	-î-	×			x	î	x	X	Ηî	X		×	î	x	X	-î	X		X	 	X		x	x	X	×	×	×	×
	x				_				x –		^	Î		- ^		Â	-	^	Â		- ^		Â		1 ^		ŵ	Ŷ		Â	Ŷ		Â
Hematology and Clinical chemistry 13			X11		_	+				+	_		+	_	-			_		_	_			_	_				х			×	
Urinelysis	×		X11					×	×			X				×			х				х.				×	×	×	×	×.	×	× .
Drug administration (MCS110 infusion) ^{14, 15}					х					х			x				X14			X ¹⁵				х									
MRI ⁴		×							x			X ¹⁸				×10			X ¹⁰				×18					х	х	X ¹⁶	×	×16	X
Corporate Confidential Information		×°																												×			X ¹⁷
Corporate Confidential Information			×		_	+ +		_	_	+ +		-	+++	_			-			_	_	-		_	-			x				-	
		-		⊢	_	+ +				+ +	_			_	-		-	_		_	_	-		_	-	-							 
	X		×			+		×				X		_		×			×	_	_	-	×		_		х	x	x	×	×	×	×
	X		×					X.				X				X			X				X X		-		X	X	X	X	X	X	X
	X			×					×			×				×			х								×	х	×	×	х	×	×
				×	×	° 2		X		X ^a	X			×	X ⁿ	X	X	X		2	< ⁿ	Xn	х	×	a	X ⁿ	×	х	X	×	×	×	×
			×	×			K 8 X	X	x		×	8 X			X ⁸	X		×	8 X			X ⁸	X			X 8	х	х	х	×	х	×	×
			×									-																x					
			×		_	+ +		-	_	+ +		+	+ +	_	-		-								-			×				-	
	X		x		-			×	×		_	X				×	-		X	-	-		X	-	-		x	Ŷ	×	×	X	×	X
			x					 	 			1 ^				Ŷ		_		-							~	ŵ	~	x		+ ^ -	Î
			x					-				-								-					-			x		Ê		-	
			- ÷			+		_			_	-		_	-		-	_		-	-			_	-			~				-	
	×		- Â	×	_			×	x		_	X				×	-	_	X	-			X		-		×	x	x	×	×	×	X
SAE reporting ⁹			~						~					_		Ŷ				_	_			_			~		~	~	~		
																x																	
Adverse Event reporting [®]					_		_	_								 	_		•								_	_	_		_		
Study completion information															1							1											×
Comments															881	require	90																
			-			4- 6	 							•																			

Novartis Amended Protocol Version v07 (Clean)

Assessment Schedule (Part C - Adolescent patients)

	CM	IC S110X	2201 Par	tC-/	۱do	lesc	ents	Ass	ess	men	t Sc	hed	ule																	
	Scree	ening	Baseline										1	Freat	nent												Fol	low-Up	,	EoS
Visit Numbers ¹	1		2		3			4		5			6			7		Т		8				9		10		12	13	777
Weeks	-		-		1			2		4			8			1	2			16				20		24	28	40	56	72
Months		-1	•					1					2			1	3			4				5		6	7	10	14	18
Study Day	- 28 to -15	5 -14 to -8	- 7 to - 1		1		1	5		29			57			8	5			113	3			141		169	197	281	393	505
Allowed visit window (days	-	-	-		-			:3		±3			±5			±	5			±5				±5		±5	±8	±8	±8	±8
Time hrs	-	-	-	pre	0 1	1 2	5	- pr	e 0	1 2	2 5	pre	0 1	2 :	5 pre	0	1 2	5	pre	0 1	2	5 pr	e 0	1	2 5					
Informed consent	×																													
Inclusion / Exclusion criteria	×		×																											
Relevant med. hist. / Current med. cond.	×		×																											
Demography	×																													
Prior / concomitant medication(s)							_	_	_		_						×													
Hepatitis B and C screen and HIV screen ¹⁵	×																													
Tuberculosis PPD skin test	×																													
Alcohol test, drug screen		×						×				×			×				×			>					×			
Pregnancy test (in serum, females only)		×					_								_														_	×
Pregnancy test (urine, females only)			×					x x				×			×				×			>			_	×				
Physical examination	×		×					××				×		+	×		_		×		+	>			_	×	×	×	×	×
Joint Range Of Motion	×		×		_			××			_	×		+	×	+	_		×	_	+	>		+	_	×	×	×	×	×
Body height	×				_						-			+			_				+	- I -		+	_					
Body weight Vital Signs: Body temperature, Blood pressure, Pulse	×		×					x x				X	V ²		X		2 20		×			×>		12		X	×	×	×	×
ECG evaluation ²	X		X	X	 	X	× .	x x x x			××	X	X -	- X	< X X	1 X	- `		XX	X^2	×	-13			XX	××	Â	×	×	×
ECG evaluation -	 	×	 	1 x	+	-^-		$\hat{\mathbf{x}}$			 	x			÷	+	-^		Ŷ	-	-	15			~	÷	Â	x	÷	×
Hematology and Clinical chemistry 12				×	+			$\hat{\mathbf{x}}$			-			+	Ť		_		x	-	+	-15		+	_	÷	Â			
Urinalysis		×						~ ^	_		-	x		+ +	- ×		2			- 14	-		_		_	 	^	X	×	×
Drug administration (MCS110 infusion) ^{13, 14}					×	-	_	_		×			×			X1	-			X ¹⁴		_		×	_	-				
MRI ⁴	×							×	٢						×10				X								×	×	×16	X
Corporate Confidential Information			×																										×	×5
	×		×					x x				X			X				X							×	×	×	×	×
	×		×					××	<			\times			×				×				< 🗌			×	×	×	×	×
				X											×											×	×	×		×
				×	×	-8									×		×			×	5	×*		X ⁶		×	×	×		×
				×		6	-		-	++	-			+			- 0			-		2	-			×	×		-	×
			×		-	·	_	_	-		-			++	-	+ +	-		-+	_	Τí	\sim	-	+ +	_	^	Â		-	~
					-		-	-	-		-				-	+	-		-	-		-			-				-	-
			×				_	-			-						-								_		×			
		×		×	-		-	×	-			×		+	×	+	-		×	-		>			_	×	×	×	×	×
			×																								l ×			
			~																											
					T																									×
SAE reporting ⁹															×															-
Adverse Event reporting [®]															×															
Study completion information															1															×
							_	-						20.0	auire		_					-			_					
Comments														as r	squire	a De														

¹ Visit structure given for internal programming and vendors programming purpose only.

² Vital signs will be monitored every 15 minutes (± 5 minutes) during the infusion.
³ During the study 12-lead ECG's should be conducted prior to blood collection.

Novartis	
Amended Protocol Version v07	(Clean)

Assessment Schedule (Part C – re-dosing)

	CMCS1	110X220	1 P a	art C	- Re	dosi	ng /	Ass	ess	me	nt S	Sche	dule	•														
	Relapse diagnosi s (RLP)	Redosing Screening 2										Redo	sing T	reatm	ent									Redo	Redosing Follow			
Visit Numbers ¹	1	2	3			4	5				6				7				8				9			12 9	777	
Visit Numbers for Cried Programming	401	402	403			404		405			406			407				408				409			411	412 °	781	
Weeks	-	-	1			2			4			8		12			16				20			28	40	56	72	
Months	-	-1	1			1					2			3				4				5			10	14	18	
Study Day	-	-7 to -1	1		15		29			57			85			113			141			169	281	393	505			
Allowed visit window (days)	-	-	-		±3		±3			±5			±5			±5				±5			±5	±8	±8	±8		
Time hrs	-	-	pre	0 1	2 6	5 -	pre	• 0	1 2	6	pre	0 1	2 5	pre	0 1	2 5	pre	0	1 2	2 6	pre	0 1	2 6	i –	-	-	-	
Informed consent	x																											
Inclusion / Exclusion criteria		×																										
Relevant med. hist, / Current med. cond.		×																										
Prior / concomitant medication(s)						_								×							
Hepatitis B and C screen and HIV screen ¹³		×																										
Tuberculosis test 14		×																										
Alcohol test, drug screen		X					X				×			×			×				×							
FSH test (females ≿18 years only)		x																										
Pregnancy test (in serum, females only)		X																									×	
Pregnancy test (urine, females only)						X	X				×			X			×				X			×				
Physical examination		X				X	X				×			×			×				×			×	X	×	×	
Joint Range Of Motion		X				X	X				×			X			×				×			×	X	×	×	
Body height		X																										
Body weight		×				X	X				×			×			×				×			X	X	×	×	
Vital Signs: Body temperature, Blood pressure, Pulse		×	×	X°	X >	K X	×	×	• X		×	×°	XX		XB	XX	×	X '	•)	к х	×	X°	XX	(X	×	×	×	
ECG evaluation 3		X	X		X	X	X		X		×		X	×		X	×)	×	×		×	×	X	×	×	
Hematology and Clinical chemistry ⁴		×				X	×				×			×			×				×			×	×	×	×	
Urinalysis		x				X	x				×			×			×		_	_	×			×	×	×	×	
Drug administration (MCS110 infusion) ⁶				×								x			×			×		_		×						
			_	 	++	_		1	•	-	-	 			-î-			-î	-	_		- î				×17		
MRI ^{7, 12}					\vdash	_	×						\square	×			×	_	_	_			+	×	×	×''	×	
Corporate Confidential Information																				_							X ¹⁰	
		×				×	×				×			×			×				×			×	×	×	×	
		x				X	X				×			×			×				X			X	X	×	×	
			X				X				×			×							×			×	X	×	X18	
			×	X ¹⁸			X				×	X18		×		X ¹⁸		2	(18	×18	×	X	8	×	X	×	X ¹⁵	
			x	X ¹⁸		_	x				×	X ¹⁶		×		X ¹⁸		-	(19	×18		X		×	×	×	X ¹⁵	
			~	X···	\vdash	_	~			-	^	X		^		X		- 2	(X	~	X	_	^	^	~	X	
					\vdash	_	-					_	\vdash					_	_	_			+	-				
																								×	×	×	×	
																								X15			X ¹⁵	
											_								-									
				-	++	-	-											-	-	_	-			-	-	-	X ¹⁸	
			X ¹⁵	_		-	X10		_			- 10		X ¹⁵			×15		-	-	X ¹⁵				1.15	×15	X ¹⁵	
			X.,				X.,				X ¹⁵	X10		X			X				X			X15	X15	X10	X	
SAE reporting *	L											×																
Adverse Event reporting ⁵							1	1 1		1 1													1 1				- -	
Study completion information Comments											-	requi															×	
Gourneus		Corr				~ .			-				-Cu															

1 Introduction

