³ During the study 12-lead ECG's should be conducted prior to blood collection.

⁴ Dosing should occur within 8 days after site received MRI validation from the vendor, infusion duration 1hr +/- 10 mns.

⁵ Two sequencial MRIs will be carried out at this visit.

Corporate Confidential Information

⁷ PK Blood for MCS110: All post-dose samples to be taken after end of infusion. The "1 hr" time point should be taken immediately after the end of infusion.

⁶ These samples are not required to be taken fasting.

⁹ SAE reporting from time of signing informed consent until 30 days after subject has stopped study participation.

¹⁰ AEs to be reported from time of first study drug administration on Day 1 until study completion.

¹¹ Alcohol and drug screen, pregnancy test, hematology and clinical chemistry : screening results can be used at baseline if baseline is planned in the next 7 days following screening.

Corporate Confidential Information

¹⁵ Hematology and clinical chemistry for safety purpose will be analyzed locally before any dosing day. Any other visits saftey samples will be analyzed by the central lab

¹⁶ At week 12, after dosing, patient's treamtment will be unblinded.

If Day 1 treatment is placebo, Assessment Schedule B1 will be applied from the next visit.

If Day 1 treatment is MCS110 Assessment Schedule B2 will be applied from the next visit Corporate Confidential Information

¹⁸ For Part B1 patients, an unscheduled visit 8 should be planned 4 weeks after visit 8 (week 20) as administration day of dose 5.

For Part B2 patients, an unscheduled visit 7 should be planned 4 weeks after visit 7 (week 16) as administration day of dose 5.

¹⁹ Collection of these samples is discontinued as of 30-Aug-2016

²⁰ Visit 109 (Part B1) will not be performed if patients had visits optional dosing visits 116 and 117 (schedule B1)

²¹ Visit 208 (Part B2) will not be performed if patients had visits optional dosing visits 215 and 216 (schedule B2). Corporate Confidential Information

Assessment Schedule (Part B – re-dosing)

	RLP	redosing Screening									R	(edo	sin	g Tr	eatr	men	t											Redo	sing Fo	ollow-up visit	EoS
Visit Numbers	1	2		3	1	4	Τ		5			6	6			7	7				8		Γ		9			10	11	12 (optional) ¹³	777
Visit Numbers for Crned Programming ¹	301	302		30	3	304	4	3	05			30	-			30				-	08				309			310	311	312 (optional) ¹³	780
Weeks	-	-		1		2			4				3			1					16				20			24	36	48	60
Months									1			2	2				3				4		Γ		5			6	9	12	15

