3.2 Part B and C

3.2.1 Study Design Part B

The study CMCS110X2201 Part B is a randomized, double-blind, placebo-controlled, parallelarm, exploratory PoC clinical trial with 2:1 randomization of MCS110 to placebo for the first dose followed by open-label multiple doses. Part B first dose will be administered double-blind, placebo-controlled. All patients will receive active treatment after the first dose and the study will continue as an open label study.

Day 1 blinding will be maintained until week 12, which corresponds to the fourth dose for the potential Day 1 MCS110 patients. After patient reaches week 12 (Visit 7), Day 1 treatment received by the patient will be un-blinded in order to allow Day 1 placebo patients to receive a fourth dose of MCS110.

If patient received placebo at Day 1, then, the patient will follow Assessment Schedule Part B1 after Visit 7.

If patient received MCS110 at Day 1, then, the patient will follow Assessment Schedule Part B2 after Visit 7.

In the multiple dose Part B patients receive up to 4 doses of 10 mg/kg MCS110 administered once every 4 weeks. Two additional MCS110 doses will be administered, if MCS110 is well tolerated and if a reduction in tumor volume of >50% can be demonstrated after the 3^{rd} MCS110 dose by MRI taken before the 4^{th} dose.

Confidential

The primary outcome of Part B of the study will be tumor volume after multiple doses of MCS110 monitored by MRI. The primary outcome will be assessed 8 weeks after the last dose of MCS110, a time point, where free drug is expected to decline rapidly, based on modeling and simulations of free MCS110 concentrations.

Patients who meet the eligibility criteria at screening will be admitted to baseline evaluations. All baseline safety evaluation results must be available prior to dosing. Safety assessments will include physical examinations, ECGs, vital signs, standard clinical laboratory evaluations (hematology, blood chemistry, urinalysis) adverse event and serious adverse event monitoring. This study will be carried out primarily in the out-patient setting.

In order to monitor the duration of the tumor size reducing effect of MCS110, patients will have follow-up visits every 3 months for up to 2 years to document changes in growth of the residual tumor or to detect recurring tumor by MRI. The time intervals of 3 months are according to the standard of care for patients, who had undergone surgery.

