In case of relapse or regrowth of residual PVNS tumor during the follow-up period, patients will be offered to start another treatment course once the previous MCS110 treatment was longer than 6 months ago (Figure 3-3), then the patient will follow Assessment Schedule Part B re-dosing. At any time during the study, investigator and/or patient can decide to undergo surgery if patient's PVNS conditions require such a treatment.

Total enrollment in the study (Part A and Part B) will proceed until up to 18 evaluable patients have been recruited, where Part B "evaluable" patient is defined as completing the protocol until at least 2 doses of MCS110 were administered and a follow-up MRI was performed. Patients will only be eligible for the study, if they have at least one tumor site that can be measured by MRI. MRI of PVNS provides unique features depicting the extent of the tumor, synovial proliferation, joint effusion, bone erosion and deposits of hemosiderin (Cheng et al 2004; Steinbach et al 1989; Frick et al 2007; Murphey et al 2008). Part A is completed, seven patients received a single dose of MCS110 or placebo. In the multiple dose Part B, patients can be treated with up to 6 doses of MCS110 following IRB approval of the amended protocol CMCS110X2201-v04.

[figure not shown]
[figure not shown]
[figure not shown]

Figure 3-2 Study design Part B

Dosing day – 1hr i.v. infusion
 Primary Endpoint – Tumor volume reduction measured by MRI [Time-point: last MCS110 dose + 8 weeks]
 Follow-up on relapse every 3 months until up to 2 years based on MRI and symptoms
 Double-blind: only at Day 1 – Day 1 Double blind maintained until week 12

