3.3 Rationale for dose/regimen, duration of treatment (Parts A and B and C)

For this first study in patients the dose of 10 mg/kg of MCS110 has been selected as the dose that had initially been identified as the highest tolerated single dose Corporate Confidential Information

In addition, a single dose of 10 mg/kg demonstrated pharmacodynamic effects suggesting target suppression up to 42 days, a 40% reduction in monocyte counts, and 80% reduction in bone resorption marker CTX-1 for at least 28 days.

MCS110 is administered by i.v. infusion, which is appropriate as the tumor is highly vascularized. By using the highest dose tolerated, we expect to maximize exposure of drug within the tumor, thus giving patients the best chance for a clinical benefit if there is one. Corporate Confidential Information

Therefore, patients

included in Part A of the proposed study are carefully monitored and appropriate dose adjustment to lower the dose is included in the protocol Corporate Confidential Information

In addition, all other potential adverse events will also be carefully monitored. There is no BMI limit for the patients to allow also obese patients to participate and potentially benefit from the study. As a monoclonal antibody, MCS110 is expected to largely distribute into blood and extra-cellular fluid spaces and then is expected to enter the highly vascularized tumor. In Part A no dose cap was applied in order to not underdose patients with a body weight higher than 100 kg and maintain sufficient exposure at the target site for 28 days.

The follow-up period is planned to be 4 weeks, which is within the general time frame between diagnosis of PVNS and surgery. Corporate Confidential Information

Corporate Confidential Information

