5.4 Treatment blinding

Part A and first dose Part B

This is a double blind study: patients, investigator staff (except the unblinded pharmacist), persons performing the assessments, and data analysts will remain blind to the identity of study treatments according to the specifications provided in Appendix 2.

A safety review will be carried out after each patient completes the 4-week treatment period, therefore the independent safety reviewer will be unblinded on an ongoing basis.

Randomization data are kept strictly confidential until the time of unblinding for the respective person(s). Further information regarding blinding and unblinding is presented in Appendix 2. The identity of the treatments will be concealed by the use of study drugs that are all identical in packaging, labeling, schedule of administration and appearance. Unblinding will only occur in the case of patient emergencies (see Section 5.5.10), at the time of the interim analysis and at the conclusion of the study.

Part B

Double-blind study part will be followed by an open label part from the second to the sixth dose.

Day 1 treatment will be maintained double blinded until week 12. At week 12, Day 1 treatment will be un-blinded in order to allow Day 1 placebo patients to receive two more MCS110 doses in open label.

Part C

28 weeks double-blind treatment period study part will be followed by an open label part.

Day 1 treatment will be maintained double-blinded until primary endpoint reached at Week 28 (or until any premature primary endpoint) to the Novartis clinical team and the investigator.

Following week 12 MRI, Novartis independent statistician (independent from the clinical study team) will proceed to the un-blinding and will share allocated dose level with an unblinded Novartis medical person (independent from the clinical team) who will review patient's safety profile and tumor volume reduction. The unblinded medical person will determine if the patient fulfills dose change conditions. The site's unblinded pharmacist will be informed by an independent study team member of potential dose change.

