If a patient develops periorbitalswelling, subsequent dosing (e.g., 4 wks, 8 wks) will be put on hold until one week after the swelling has resolved.

If a patient develops any adverse event considered as drug related by the investigator, which has not resolved before the following dose, next dosing will be delayed until considered resolved.

If there are abnormal hematology and / or biochemistry laboratory values (CTCAE grade 3) judged as clinically significant by the Investigator, the next dose will be delayed until abnormalities have resolved. Isolated CK increase with normal troponin T and aldolase is not considered a safety concern even if reaching CTCAE grade 3.

Part B: If dosing of 4 times 10 mg/kg MCS110 (once every 4 weeks) is exceeding the initial 13 weeks dosing period, (due to occurrence of AEs) further dosing will be allowed up to week 20 if all AEs had resolved for more than a week and efficacy assessment demonstrates response to treatment (>50 % of tumor volume reduction after 3^{rd} dose in Part B, 45% in Part C) of these patients.

Dosing extension to 6 consecutive doses once every 4 weeks

Patients initially receive 4 consecutive doses once every 4 weeks (week 0, 4, 8, 12). Patients will receive 1 or 2 additional doses under the following conditions:

- no treatment related safety issues (for periorbital swelling* only if >grade 2) resulting in dosing delay during the first 4 doses the tumor has not been completely eliminated after the 3rd dose [determined by MRI at week 12]
- the tumor did respond to treatment (Part B: >50 % tumor volume reduction) after the 3rd dose [determined by MRI at week 12] Corporate Confidential Information

In Part C additional criteria apply as following:

- Part C (arms 3 mg/kg or 5 mg/kg): the tumor did respond to treatment (≥45 % tumor volume reduction) after the 3rd dose [determined by MRI at week 12] and MCS110 was tolerated: the patient will receive 3 additional doses of the same as dose level
- Part C (arms 3 mg/kg or 5 mg/kg): the tumor response to treatment is <45 % of tumor volume reduction after the 3rd dose [determined by MRI at week 12] and MCS110 was tolerated: the patient will receive doses increased to 10 mg/kg
- Part C (arm 10 mg/kg): the tumor did respond to treatment (≥45 % tumor volume reduction) after the 3rd dose [determined by MRI at week 12] and MCS110 was tolerated: the patient will receive 3 additional doses of 10 mg/kg

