5.5.8 Prohibited treatment

Parts A and B:

Diabetes drugs, cancer drugs, immunosuppressants and biologics are not allowed.

Part C:

Cancer drugs, immunosuppressants and biologics are not allowed.

Parts B and C:

Tumor aspiration is not allowed during the treatment phase (can be performed only after 8 weeks follow-up MRI of last dose).

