5.5.12 Early study termination

The study can be terminated at any time for any reason by Novartis. Should this be necessary, the patient should be seen as soon as possible and treated as described in Section 6 for a prematurely withdrawn patient. The investigator may be informed of additional procedures to be followed in order to ensure that adequate consideration is given to the protection of the patient's interests. The investigator will be responsible for informing IRBs and/or ECs of the early termination of the trial.

6 Visit schedule and assessments

The full Part A, Part B and Part C Assessment Schedules are presented before Section 1.

Confidential

Assessment Schedule Part B after week 12, presents 2 parts to apply:

- If patient received Day 1 placebo, Assessment Schedule Part B1 applied after Visit 7
- If patient received Day 1 MCS110, Assessment Schedule Part B2 after Visit 7

For detailed instructions on the collection, handling, labeling and shipment of samples please refer to separate Laboratory Protocol and Laboratory Manual.

All blood samples will be taken by either direct venipuncture or an indwelling cannula inserted in a forearm vein.

The exact clock time of dosing, as well as actual sample collection date and time (including pre-dose samples) will be entered on the appropriate page of the eCRF. Sampling problems will be noted in the relevant field of the eCRF.

When the assessments are scheduled to be performed at the same time-point, the order of priority will be as follows: questionnaires, ECG, vital signs, blood samples, imaging biopsy and dosing.

Part A

Sampling windows

- For samples drawn on Day 1, there is a \pm 15min window.
- For samples drawn after Day 1, there is a ± 6-hour window (based on T=0 dosing start time).

Visit windows

- From Day 1 to Day 14 visits should be conducted as scheduled.
- From Day 15 to Day 28 there is $a \pm 3$ day visit window.
- From Day 33 (day of surgery) to EOS (end of study) there is $a \pm 5$ day window.

Part B

Sampling windows

- For samples drawn on Day 1 there is $a \pm 15$ min window.
- For samples drawn after Day 1, there is a ± 6-hour window (based on T=0 dosing start time).

Visit windows

- From Day 1 to Day 15 visits should be conducted as scheduled.
- From Day 15 to Day 28 there is $a \pm 3$ day visit window.
- From Day 57, Day 169 there is $a \pm 5$ day window.
- For all follow-up visits until End Of Study visit, there is $a \pm 8$ days window.

Part C

Sampling windows

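### Six-dose Part B patients have no scheduled MRI at the primary-endpoint time (last dose + 8 weeks): the nearest visible scans are 28 days early or 56 days late

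*Protocol*

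**What the plan says.** Protocol 3.2.1 states: "The primary outcome will be assessed 8 weeks after the last dose of MCS110". The legend of Figure 3-2 repeats it: "Primary Endpoint – Tumor volume reduction measured by MRI [Time-point: last MCS110 dose + 8 weeks". Other sections assume the same scan. Section 5.5.8 says tumor aspiration "can be performed only after 8 weeks follow-up MRI of last dose". The re-treatment rule in 5.5.5.2 refers to the primary endpoint 8 weeks after the last of six doses.

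Doses 5 and 6 are optional. Under 5.5.5.2 they depend on a reduction of more than 50% at week 12, on no treatment-related safety issue that delayed dosing during the first four doses (periorbital swelling counts only above grade 2), and on the condition that "the tumor has not been completely eliminated after the 3rd dose [determined by MRI at week 12".

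In schedule B2 (Day 1 MCS110), dose 6 is at week 20 and later MRIs are at weeks 24, 36, 48 and onward. In schedule B1 (Day 1 placebo), dose 6 is at week 24 and later MRIs are at weeks 28, 40, 52 and onward. Footnote 21 says "Visit 208 (Part B2) will not be performed if patients had visits optional dosing visits 215 and 216 (schedule B2"; footnote 20 does the same for visit 109 in B1.

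For Part C, Protocol 5.4 says "Day 1 treatment will be maintained double-blinded until primary endpoint reached at Week 28", and the Part C schedules have an MRI at that visit.

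SAP 7.1 (Part B*, which pools Parts B and C) plans a waterfall plot of maximum reduction by number of doses, and time-to-ablation summaries. Both run to 8 weeks after the last dose. The visible SAP gives no window or substitute visit for the endpoint scan, and 7.1.1 leaves missing data unimputed.

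**The concern.** Followed as printed, the plan has no endpoint scan for patients who receive all six doses. That group is selected on outcome: good but incomplete responders at week 12. The mistiming is therefore related to response.

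If the 4-week scan is used, these patients are read while the drug may still be acting. Protocol 3.3 reports that "a single dose of 10 mg/kg demonstrated pharmacodynamic effects suggesting target suppression up to 42 days", and 3.2.1 chose 8 weeks because free drug is expected to decline rapidly by then. Four- and five-dose patients would be read at 8 weeks.

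In the pooled Part B* outputs, the six-dose group would combine Part B patients followed for about 28 days after dose 6 with Part C patients followed for about 56. A maximum reduction taken without the 8-week scan can only be equal or smaller, and a complete ablation between the two times would be missed. With no window in the SAP, the programmer has to decide which scan counts.

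**Working it through.** **Inputs.** Dosing and MRI weeks come from Protocol schedules B1, B2 and Part C. The dose-5 visits are placed by footnote 18 (week 16 in B2, week 20 in B1). Visit windows are in Protocol 6. Day = 1 + 7 × week; scan due = last-dose week + 8; offset = scheduled MRI day − due day.

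| Course | Last dose | Scan due | MRI visits | Offset (days) |
|---|---|---|---|---|
| B2, 4 doses | week 12 | week 20 | 208, week 20 | 0 |
| B2, 5 doses | week 16 | week 24 | 209, week 24 | 0 |
| **B2, 6 doses** | week 20 | week 28 (Day 197) | 209, week 24; 210, week 36 | **−28; +56** |
| B1, 4 doses | week 16 | week 24 | 109, week 24 | 0 |
| B1, 5 doses | week 20 | week 28 | 110, week 28 | 0 |
| **B1, 6 doses** | week 24 | week 32 (Day 225) | 110, week 28; 111, week 40 | **−28; +56** |
| Part C, 6 doses | week 20 | week 28 (Day 197) | 11, week 28 | 0 |

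The plan's 8-week time is reproduced for four and five doses and for Part C, but not for six doses in Part B. (Schedule B1 prints Day 196 for week 28; by that day number the offset is −29.)

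**Can the visit windows close the gap?** Dosing visits are allowed ±5 days. The rule beginning "For all follow-up visits until End Of Study visit, there is" gives ±8 days for follow-up. Section 6 gives ±5 up to Day 169; the wider ±8 is used here for every scan.

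- B2, six doses, dose 6 on Day 141 ± 5 (136 to 146):
  - visit 209, Day 169 ± 8: (161 − 146) to (177 − 136) = 15 to 41 days after dose 6
  - visit 210, Day 253 ± 8: (245 − 146) to (261 − 136) = 99 to 125 days
- B1, six doses, dose 6 on Day 169 ± 5 (164 to 174):
  - visit 110, Day 196 ± 8: (188 − 174) to (204 − 164) = 14 to 40 days (15 to 41 if Day 197)
  - visit 111, Day 281 ± 8: (273 − 174) to (289 − 164) = 99 to 125 days
- Four doses:
  - B2, Day 85 ± 5 to Day 141 ± 8: (133 − 90) to (149 − 80) = 43 to 69 days
  - B1, Day 113 ± 5 to Day 169 ± 8: 43 to 69 days
- Five doses:
  - B2, Day 113 ± 5 to Day 169 ± 8: 43 to 69 days
  - B1, Day 141 ± 5 to Day 196 ± 8: (188 − 146) to (204 − 136) = 42 to 68 days

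Four- and five-dose scans thus fall at 42 to 69 days. Six-dose scans fall at no more than 41 or no fewer than 99 days, against the required 56.

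**Cause.** Footnotes 20 and 21 mark the place but do not create the gap. Visits 109 and 208 fall in the week of dose 6, so keeping them would not supply the missing scan. The follow-up grid fits four or five doses and is not re-timed for a sixth.

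**Re-dosing.** The Part B re-dosing table has the same pattern (last dose week 20, MRIs at weeks 24 and 36), although 5.5.5.2 calls for an MRI 8 weeks after the last dose. Its MRI footnote is blacked out.

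**The case against.** The strongest objection is redaction. Footnote 17, attached to the optional dosing visits, and text after footnote 21 are blacked out, and the design figures are not shown. An extra scan could be specified there, and the fact that 5.5.5.2 and 5.5.8 expect the scan makes this more plausible. This stands as a limit: the finding concerns the visible schedule. The MRI row itself carries no visible footnote in B1 or B2, and the SAP gives no window either way.

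The B1 half depends on a week-24 dose. Schedule B1 shows it, and Protocol 3.2.3.1 supports it (three further doses for Day 1 placebo patients). Section 5.4 says two more, and 5.5.4 lists Part B doses only to week 20. If B1 dosing ended at week 20, that would be a fifth MCS110 dose and the week-28 scan would fit. B2 is unaffected.

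Impact can also be overstated. The Part B analysis is descriptive, with no test at 8 weeks. All scans are listed, and the waterfall is already shown by number of doses. No net direction of bias is established: an early reading may catch continuing drug effect, while a truncated maximum is conservative. These points limit the severity. They do not supply the missing endpoint value or settle which scan stands for it.

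Finally, Protocol 4 describes Part B patients as in follow-up, so a schedule change may reach few or none of them in their first course. That is fair, and it is why the SAP rule is the main remedy.

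**Conclusion.** The concern holds. On the visible schedules, six-dose Part B patients have no MRI at the stated primary-endpoint time: the nearest are 28 days early and 56 days late, and the visit windows cannot bridge this. Four- and five-dose courses and Part C are unaffected. The number of six-dose patients is not stated; it lies between 0 and 11 of the 11 Part B patients. The effect on tumor volume cannot be computed from the documents. Confidence is medium because of the blacked-out text, and for B1 the conclusion also assumes the week-24 dose. The point should be corrected, because it concerns the primary time point and the pooled Part B* outputs, but it does not undermine the study as a whole.

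**What to change.** 1. **SAP 7.1.** Select the endpoint scan from the actual last-dose date within a stated window. An example is 42 to 70 days, which admits every on-schedule four- and five-dose scan and no scheduled six-dose scan. Its lower edge meets the cited 42-day suppression period, so a narrower window could be preferred, at the cost of excluding some on-schedule scans. For six-dose patients with no scan in the window, report the 4- and 16-week values separately, labelled by days since last dose, and do not pool them as 8-week values. Interpolation is at most a sensitivity analysis. Flag these patients in the waterfall and ablation outputs.
2. **Schedule.** For any six-dose patient still to be scanned, move only the MRI of visit 209 (B2) or 110 (B1) to 8 weeks after the actual last dose, and leave that visit's safety assessments in place. This matches Part C, which has an MRI at week 28 and none at week 24.
3. **Reconcile the Protocol.** The six-dose schedules must be reconciled with 3.2.1; the week-24 dosing visit in B1 with 3.2.3.1, 5.4 and 5.5.4; and the Part B re-dosing follow-up with 5.5.5.2.
4. **SAP 2.3.** It assigns B1 and B2 the opposite way from Protocol 3.2.1 and still describes at most four doses. No visible analysis uses those labels, so this is a text correction.

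The cost is SAP wording and one schedule footnote, with no additional MRI. Where a scan is moved, the 4-week post-dose MRI is lost and the patient makes a separate trip.
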